The longstanding view has been that insomnia, and other forms of sleep disturbance, emerge as a consequence of dementia and are the result of progressive neuronal damage. However, there is growing evidence that the direction of causation may go both ways, with sleep disturbance potentially increasing vulnerability to dementia. Longitudinal studies have found that sleep disturbance often precedes and increases risk for dementia by several years. The purpose of this study is to examine the relationship

between chronic insomnia and dementia biomarkers and orexin levels found in cerebrospinal fluid (CSF). Fifteen adults age 30-50 with chronic insomnia and age- and gender-matched good sleepers will undergo overnight polysomnography and CSF sampling in the morning.

Objectives

Overall objectives

Patients with dementia very frequently have disturbed sleep that is thought to be caused, in part, by the dementing illness. There is growing evidence of the reverse direction of causation, with sleep disturbance increasing vulnerability to dementia. The recently-discovered glymphatic system, by which waste from neural metabolism is cleared from the brain, may be a mechanism for the sleep-dementia link. The goal of this project is to examine the relationship between chronic sleep disturbance (insomnia) and dementia biomarkers and orexin levels as assessed in cerebrospinal fluid (CSF). Fifteen adults age 30-50 with chronic insomnia and age- and gender-matched good sleepers will undergo overnight polysomnography and morning CSF sampling. These data will be used to address the following specific aims: Specific Aim 1: To examine the association between chronic insomnia and CSF markers of dementia. Hypothesis 1: Chronic insomnia will be associated with higher levels of CSF AB markers compared to good sleepers. Specific Aim 2 (exploratory): To examine the role of orexin in mediating the relationship between chronic insomnia and CSF markers of dementia. Hypothesis 2: Higher CSF orexin levels will mediate the relationship between chronic insomnia and A markers.

Primary outcome variable(s)

Dementia biomarkers in cerebrospinal fluid

Secondary outcome variable(s)

CSF orexin levels

Background

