
the treatment of chronic insomnia.

Study Design

Phase* Not applicable

Design

Laboratory Observational study

Study duration

The total duration of the study will be 24 months, each participants duration in the study will be approximately 4 weeks.

Resources necessary for human research protection

Describe research staff and justify that the staff are adequate in number and qualifications to conduct the research. Describe how you will ensure that all staff assisting with the research are adequately informed about the protocol and their research related duties. Please allow adequate time for the researchers to conduct and complete the research. Please confirm that there are adequate facilities for the research.

The principal investigator involved in this project has extensive experience in sleep research, including having a history of success in conducting studies with CSF sampling. A study coordinator will be hired for this study and they will be trained in all designated duties and responsibilities of the study. [name] will provide oversight of the study coordinator. The study will be conducted at the CTRC, where there are sufficient facilities and resources available.

Characteristics of the Study Population

Target population

Fifteen adults age 30-60 with chronic insomnia and fifteen age- and gender-matched good sleepers.

Subjects enrolled by Penn Researchers 30

Subjects enrolled by Collaborating Researchers

0

Accrual

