Participants will be recruited through targeted advertisements in the Philadelphia area community. We have a track record of success in recruitment through these approaches. To estimate the appropriate sample sizes, statistical calculations were carried out using pilot data obtained from OxA and ABO measurements from N=6 individuals. Specifically, two-sided two-sample t-test was utilized for a two-group parallel design study which compared chronic insomniacs with good sleepers. For OxA, sample sizes needed to detect intended effect sizes (differences of 30%, 40%, and 50) were estimated at 80% power. For ABO, sample sizes were calculated to significantly detect the differences between two groups of 50%, 100%, and 150% at 80% power. Power calculations were performed on OxA and ABO in raw and natural log scales, respectively, after examining the normality of data with residual plots. Variability estimates at each time point were obtained as averages of sample standard deviations of two treatment groups per time point. As such, N=15/group would be sufficient to identify changes in the 8 AM samples considering effect sizes equal or greater than 30% and 100% for OxA and ABO, respectively.

Key inclusion criteria

All subjects must meet the following criteria: -Age 30-60 -Men and women To be included in the insomnia group, subjects must meet the following DSM5 Diagnostic Criteria for insomnia disorder: - dissatisfaction with sleep quantity or quality (difficulty initiating or maintaining sleep, or waking up too early) despite adequate opportunity for sleep -sleep disturbance causes clinical significant distress or impairment in functioning -present at least 3 times per week for at least 3 months -sleep disturbance is

not better explained by a medical or psychiatric condition or based on the effects of a substance - Insomnia Severity Index (ISI) score 14 or greater.

Key exclusion criteria

-Diagnosis or evidence of sleep disorders other than insomnia as determined by the screening questionnaires and clinical history -Women who have been pregnant or lactating within the past six months -Non-fluency in spoken or written English -Current or past month shiftwork defined as working during the evening or night shift -Current use of medications or OTC products that impact sleep - Evidence of neurological abnormalities that could include the risks associated with lumbar puncture (e.g.papilledema, mass lesion, Chiari malformation).

Vulnerable Populations

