
The following documents are currently attached to this item:

There are no documents attached for this item.

Deception

Does your project use deception? Deception could be considered any direct misinformation presented to the subject or omission of key information pertaining to the design or nature of the project. No

International Research

Are you conducting research outside of the United States? No

Analysis Plan

Paired-samples t-tests will be conducted to compare each of the CSF analytes between patients with chronic insomnia and matched good sleepers. Multiple regression analyses will be used to examine whether CSF orexin levels mediate the relationship between chronic insomnia and AB markers. Mediation analyses will be conducted using a series of linear regression models in which group (insomnia or control) and orexin levels will be treated as independent variables and AB markers will be treated as the dependent variables.

The following documents are currently attached to this item:

There are no documents attached for this item.

Data confidentiality

- x Paper-based records will be kept in a secure location and only be accessible to personnel involved in the study.
- x Computer-based files will only be made available to personnel involved in the study through the use of access privileges and passwords.
- x Prior to access to any study-related information, personnel will be required to sign statements agreeing to protect the security and confidentiality of identifiable information.
- x Wherever feasible, identifiers will be removed from study-related information.

A Certificate of Confidentiality will be obtained, because the research could place the subject at risk of criminal or civil liability or cause damage to the subject's financial standing, employability, or liability.

A waiver of documentation of consent is being requested, because the only link between the subject and the study would be the consent document and the primary risk is a breach of confidentiality. (This is not an option for FDA-regulated research.)

Precautions are in place to ensure the data is secure by using passwords and encryption, because the research involves web-based surveys.

Audio and/or video recordings will be transcribed and then destroyed to eliminate audible identification of subjects.

Subject Confidentiality

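### The Aim 2 mediation regressions leave out age and sex, which matching balances between the groups but not within them, so the orexin–AB coefficient can be confounded

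*Combined protocol and SAP*

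**What the plan says.** The Analysis Plan has two parts. For the group comparisons, "Paired-samples t-tests will be conducted to compare each of the CSF analytes between patients with chronic insomnia and matched good sleepers". For mediation, it describes a series of linear regressions in which "group (insomnia or control) and orexin levels will be treated as independent variables and AB markers will be treated as the dependent variables". No covariate and no matched-pair term is named for the regressions, and no other section adds one.

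The Objectives section states the aim as "Specific Aim 2 (exploratory): To examine the role of orexin in mediating the relationship between chronic insomnia and CSF markers of dementia". Its hypothesis is directional: "Higher CSF orexin levels will mediate the relationship between chronic insomnia and A markers" (a character after the A was probably lost in the text).

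Age and sex are handled by matching alone. The Abstract and Objectives describe "Fifteen adults age 30-50 with chronic insomnia and age- and gender-matched good sleepers". The Target population entry reads "Fifteen adults age 30-60 with chronic insomnia and fifteen age- and gender-matched good sleepers", and the Key inclusion criteria read "All subjects must meet the following criteria: -Age 30-60 -Men and women". So each group contains men and women spread over 20 or 30 years of age, depending on which range applies. Under Procedures, demographics are collected at the initial visit.

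**The concern.** Mediation needs two links: insomnia to orexin, and orexin to AB. Matching makes age and sex independent of group. That protects the first link and the overall insomnia–AB comparison. It does not make age and sex independent of orexin among people in the same group, and that is where the second link is estimated once group is in the model. An age or sex trend shared by orexin and AB therefore enters the orexin coefficient.

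The paired t-test on orexin cannot repair this, because it tests the first link. Hypothesis 2 rests on the second. If age or sex moves both analytes in the same direction, a real insomnia–orexin difference with no orexin effect on AB could be read as mediation. If it moves them in opposite directions, real mediation could be masked.

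**Working it through.** **The plan's own figure.** The documents give no effect size or power for Aim 2. The only sizing statement, under Accrual, is that "N=15/group would be sufficient to identify changes in the 8 AM samples considering effect sizes equal or greater than 30% and 100" per cent for OxA and ABO respectively. It rests on a two-sided two-sample t-test at 80% power. Alpha is not stated; I assume 0.05. With 15 per group the detectable standardised difference is √(2/15) × (1.960 + 0.842) = 1.02 by the normal approximation, and 1.06 from the noncentral t with 28 degrees of freedom. That implies an OxA coefficient of variation of at most 0.30/1.06 = 0.28 and an ABO log-scale SD of at most ln 2/1.06 = 0.65. The pilot SDs are not printed, so the figure can be neither confirmed nor refuted. The point here does not depend on it.

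**Bias.** Let Z be age (or sex), standardised and identical within a matched pair. Within a group, scale orexin and AB to SD 1 and let their correlations with Z be r1 and r2. If orexin has no effect on AB, the slope of AB on orexin given group is Cov(orexin, AB)/Var(orexin) = r1 × r2. It is zero if either correlation is zero. If age and sex both act and are uncorrelated, the products add: 0.3 for each factor with each analyte gives 0.09 + 0.09 = 0.18.

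**False-positive rate of the orexin coefficient.** I simulated 15 exactly matched pairs with uniform ages, a true orexin effect of zero, and a two-sided test at 0.05. The correlations are assumptions.

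| Correlation of age with each analyte | Bias, r1 × r2 | Group and orexin only | Plus age and sex |
|---|---|---|---|
| 0 | 0 | 5% | 5% |
| 0.2 | 0.04 | 5.5% | 5% |
| 0.3 | 0.09 | 7% | 5% |
| 0.4 | 0.16 | 13% | 5% |
| 0.5 | 0.25 | 26% | 5% |

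Sex in place of age gives nearly the same rates. Correlations of −0.4 and 0.4 give a bias of −0.16 and again about 13%. Correlations of 0 and 0.5 give no bias and about 5%. Unequal values of 0.5 and 0.2 give a bias of 0.10, close to the 0.3 row.

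**Effect of the two age ranges.** Under uniform ages the SD of age is 30/20 = 1.5 times larger for 30–60 than for 30–50. A per-year slope that gives a correlation of 0.3 over 30–50 has a signal-to-noise ratio of 0.3/√(1 − 0.09) = 0.314. Times 1.5 this is 0.472, and the correlation becomes 0.472/√(1 + 0.472²) = 0.43. The wider range would therefore move a study from the 0.3 row to between the 0.4 and 0.5 rows.

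**Cost of adjusting when age and sex have no effect.** Residual degrees of freedom are 30 − 3 = 27 as planned and 30 − 5 = 25 with age and sex. Take a true partial correlation of 0.5, which is a slope of 0.5/√0.75 = 0.577. Power for the orexin coefficient falls from about 81% to 78%. Requiring both links to be significant, with a 1.06 SD orexin difference, power falls from 64.4% to 61.7% if both links come from regressions, and from 61.5% to 59.1% if the paired t-test is kept for the first link.

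**The case against.** The strongest reply is that the harm is hypothetical. Nothing in the documents shows that age or sex is related to either analyte in this population. At 0.2 the effect is negligible, at 0.3 it is small, and material inflation needs about 0.4 or more with both analytes. That stands, and it is why the size can only be given as a range. A reader might infer that the plan carries a false-positive rate of 13% or 26%. The documents do not support that.

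Second, the plan states no decision rule for mediation. If both links must be significant, the false-positive rate also depends on how large the insomnia–orexin difference is. With an assumed difference of 1.06 SD the joint rate is about 6%, 11% and 23% at correlations of 0.3, 0.4 and 0.5. With 0.5 SD it is about 2% at 0.3 and 9% at 0.5. That also stands, so the figures relied on here are for the orexin coefficient alone, which need no such rule.

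Third, Aim 2 is labelled exploratory, and the plan names no covariates without excluding them. This limits the weight of the point, but exploratory status does not remove bias. Choosing covariates after seeing data on 30 people would invite selective adjustment.

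**Conclusion.** The point holds as a cheap improvement confined to exploratory Aim 2. The stated model leaves the orexin–AB coefficient open to confounding by the two factors the study chose to match on. The bias is about the product of their correlations with orexin and AB. It ranges from negligible at 0.2 to substantial at 0.5, under assumed correlations, exact matching and linear effects.

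Two stronger readings should be avoided. A reader might infer that the Aim 1 comparison is confounded as well. It is not, because matching balances age and sex between the groups and the planned test is paired. A reader might also infer that adjustment would make the mediation claim secure. It would not: other common causes of orexin and AB would remain, and the data are cross-sectional.

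**What to change.** In the last sentence of the Analysis Plan, name age and sex as covariates in the Aim 2 regressions:

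- orexin on group, age and sex;
- each AB marker on group, orexin, age and sex.

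Add that a positive finding will be described as consistent with mediation, because other confounders of orexin and AB are not controlled.

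The cost is two degrees of freedom, a linear age term, and the 2.5 to 3 points of power shown above if age and sex turn out not to matter. No new data are needed, since both variables are required for the matching. A matched-pair term would also remove the bias, but it leaves 30 − 17 = 13 residual degrees of freedom against 25, so the two covariates are the better choice with 15 pairs.
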